11.5.1. Adverse Event Notification On or Prior to the 90-day Follow-up Visit

Ninety days (with ± 45 days visit window allowed) after the S-ICD implant and test procedure the subject will either visit the investigator's clinic or be contacted by phone from the investigator or delegated staff to check on their health status. A chart review will also be performed.

If the following adverse events occur on or prior to the subject's 90-day follow-up visit, they shall be communicated within 24 hours of awareness to Boston Scientific clinical study team:

- subject death
- S-ICD system infection
- excessive bleeding that requires medication, transfusion, or the use of blood derivatives
- unplanned hemodynamic/cardiovascular support

Boston Scientific Medical Safety will conduct a safety review and may request additional event information to facilitate its review. Boston Scientific shall communicate to all investigators if subject enrollment and implant procedures shall be postponed pending further safety review and will communicate to all investigators when enrollment and implant procedures could resume after the safety review is completed.

Any study reportable adverse events that have not been reported previously will be submitted on the Adverse Event case report form (CRF). See Section 20.1 for a summary of all reportable adverse events in the study.

11.6. Study Completion

A subject's participation in the study will end after completion of the 90-day follow-up visit. After completion in the study, subjects will be followed per standard of care.

11.7. Source Documents

Participating investigators must maintain original source documents that are accurate, complete, and current related to the subject's participation in this study. Source documentation must include but is not limited to those listed in Table 11-2:

Table 11-2: Source Documentation Requirements

Requirement	Disposition

• Signed informed consent forms for each enrolled subject• S-ICD pre-implant screening report• Demographics, medical history and medication use per center's subject records (EMR, etc.)• Physical assessment including height and weight• Acute procedure data Technical Source Form• Adverse events and device deficiencies• If VF conversion test was performed: Induced VT/VF episode and Induction Report for all episodes shocked• Programmer Printouts:
- Final Summary Report- Device Episode Report(s), if applicable• Reportable Adverse Events, Device Deficiencies, and Protocol Deviations if applicable	Retain at site

• Fluoroscopic images or X-rays, if taken in-procedure, or post-operatively, to	Retain at site and send a copy to Boston Scientific

Table 11-2: Source Documentation Requirements

Requirement	Disposition
confirm the electrode and pulse generator locations	

Save S-ICD programmer log files to SD card at the completion of the acute testing	Retain SD card at site and transfer data electronically to BSC via LATITUDE Link or Camelion Server

12. Statistical Considerations

12.1. Study Data

12.1.1. Primary Data and Secondary Data

Primary Data

1. Safety: All device- and procedure-related adverse events through 90 days post-implant procedure.
2. Effectiveness: defibrillation threshold (DFT) of the two-electrode shock configuration - two left-parasternal electrodes to the left lateral PG.

Secondary Data

1. Shock impedance of the electrode conversion tests using both the single electrode (at 65 J) and the 2-electrode configurations (Parallel and 90°).
2. Percentage of defibrillation success of VF conversion at each of the tested energy level

Hypotheses

This is an early-stage feasibility study. There is no formal hypothesis due to study not being powered for its sample size and no control group for comparison. This study seeks to characterize the performance of the new electrode shock configuration by collecting defibrillation conversion and shock impedance data.

Sample Size

This is an early-stage feasibility study and there is no formal sample size calculation. It is estimated that 20 subjects with complete testing, within an electrode configuration, will allow for a reasonable confidence in assessing defibrillation performance. For example, if 19 out of 20 subjects are successfully converted at 50 J (95% success) the resulting 95% confidence interval will be 75.13% to 99.87% using exact test, which is considered acceptable for this early feasibility assessment.

Since some enrolled subjects may not start and/or complete testing due to a variety of reasons, including exceeding the protocol-required safety criteria per Sections 11.4.2 and 11.4.3, and since a protocol revisions was made to add testing of a 2nd 2-electrode configuration (90° configuration), the study will enroll up to 42 subjects so that 30 complete datasets can be expected.

Statistical Methods

This is an early-stage feasibility study to assess performance of the new electrode shock configurations. No specific statistical tests will be performed. Descriptive statistics will be provided as follows,

- Subject demographic and medical history data will be reported as raw numbers and percentage for categorical variables and mean ± standard deviation for continuous variables.
- DFTs and shock impedances will be reported as mean ± standard deviation.
- Defibrillation success at a given energy level (eg 50 J, etc.) will be reported as a percentage and 95% confidence interval.
- System and procedure related adverse events occurrence and percentage will be collected and reported starting from the time of the subject enrollment.

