	
2 additional VF inductions and shocks per the protocol specified testing sequence. After testing is completed in the first configuration, the second configuration will be tested using 2 additional VF inductions. Lastly, after the DFT testing is completed, the second S-ICD electrode and Investigational S-ICD Y-Adapter are disconnected and removed, and the S-ICD system implant is completed per investigator's usual practice and experience.
 
A schematic representation of the Investigational S-ICD Y-Adapter and the electrode/PG connection during investigational testing is shown below. The second electrode is either parallel to the first with 0.5-2 cm spacing (left figure) or is inserted at an ~90 degree angle from the first (right figure).
 
Planned Number of Subjects	A maximum of 42 subjects will be enrolled to obtain at least 30 complete datasets.
Planned Number of Investigational Sites / Countries	A maximum of 10 sites are allowed in Europe and possibly in the United States.
Primary Safety Data	All S-ICD system and procedure related adverse events

**Acute Feasibility Investigation of a New S-ICD Electrode Arrangement
for Reduction of Defibrillation Energies**

[ASE Study]

Primary Effectiveness Data	Defibrillation Threshold (DFT) of the 2-electrode configuration (Parallel and 90°)
Additional Data	
• VF conversion success for the 2-electrode configurations (Parallel and 90°)• Shock impedance of both the one- and 2-electrode configuration (Parallel and 90°)
Method of Assigning Subjects to Treatment	All enrolled subjects are intended to have the 2 nd electrode inserted and undergo acute testing. The order of 2-electrode configuration (Parallel and 90°) testing will be alternated based on the subject's ID # to help reduce the possibility of a test order bias.
Follow-up Schedule	Study procedures/visits will occur at the following time periods: 
• Consent and enrollment visit• S-ICD implant procedure visit• 90-day follow-up visit (to be conducted in clinic or by telephone at 90±45 days post-implant)
Study Duration	Duration of the study, from the first enrollment to the last subject's final visit is expected to be approximately 20-28 months. Individual subjects will be followed from enrollment until their 90-day follow-up visit.

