11.1. Data Collection

Data are collected at the following time points specified in Table 11-1. Reportable adverse events and device deficiencies are reported on an ongoing basis and throughout a subject's participation of the trial.

Table 11-1: Data Collection Schedule

Procedure/Assessment	Enrollment Visit	S-ICD Implant Procedure Visit (within 30 days after Enrollment)	90-day Follow-up Visit (90±45 days Post-implant)
Informed consent form, including informed consent signature and date	X		
Demographics, including date of birth, gender, and race and ethnicity	X		
Physical assessment, including weight and height	X		
Medical history and current medication	X		
S-ICD System information and implant data collection		X	
65 J VF conversion test (one-electrode configuration) data collection		X	
Acute DFT Testing (2-electrode configuration (Parallel and 90°) data collection, including:		X X	
• Temporary insertion of the second electrode and documentation of electrode locations with fluoroscopy (saved images)			
Transfer of S-ICD firmware and programmer log files		X	

Table 11-1: Data Collection Schedule

Procedure/Assessment	Enrollment Visit	S-ICD Implant Procedure Visit (within 30 days after Enrollment)	90-day Follow-up Visit (90±45 days Post-implant)
Post-operative x-rays, if standard of care		X	
Adverse events/device deficiencies*	Collected throughout the trial starting from the time of the subject's enrollment		

X = required

*See Section 20.1 for a summary of reportable adverse events in the study.

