The risk to benefit ratio for this study is reasonable because the subject is already undergoing an S-ICD implant that includes sedation and/or anesthesia, insertion of a subcutaneous electrode and VF conversion testing. Since the standard implant and VF conversion test will be done prior to investigational procedures, it provides a high degree of assurance that the VF conversion testing is well tolerated. The protocol includes criteria to exclude subjects from the investigational testing should the initial standard of care VF conversion test suggest that the subject may be at higher risk for adverse events.

20. Safety Reporting

20.1. *Reportable Events by investigational site to Boston Scientific*

It is the responsibility of the investigator to assess and report to Boston Scientific any event which occurs in any of following categories:

- All Serious Adverse Events regardless of cause

- All Device and/or Procedure Related Adverse Events regardless whether considered serious or not
- All Device Deficiencies
- Unanticipated Adverse Device Effects (UADE) /Unanticipated Serious Adverse Device Effects (USADE) previously not defined in the physician's manual
- Certain adverse events must be reported to the sponsor in a shortened time frame, per Section 11.4.6 and 11.5.1.
- New findings/updates in relation to already reported events

When possible, the medical diagnosis should be reported as the Event Term instead of individual symptoms.

If it is unclear whether or not an event fits one of the above categories, or if the event cannot be isolated from the device or procedure, it should be submitted as an adverse event and/or device deficiency.

Any reportable event, experienced by the study subject after informed consent and once considered enrolled in the study (as defined in study subject classification Section 10.3), whether prior to, during or subsequent to the study procedure, must be recorded in the paper CRF.

Underlying diseases and chronic conditions are not reported as AEs unless there is an increase in severity or frequency during the course of the investigation. Death should not be recorded as an AE but should only be reflected as an outcome of ONE (1) specific SAE (see Table 20.2-1 for AE definitions).

Refer to Section 19 for the known risks associated with the study device(s).

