Device Deficiencies (including but not limited to failures, malfunctions, and product nonconformities) Note: Any Investigational Device Deficiency that might have led to a serious adverse event if a) suitable action had not been taken or b) intervention had not been made or c) if circumstances had been less fortunate is considered a reportable event.	Complete Device Deficiency CRF with all available new and updated information.	
 Within 3 calendar days of first becoming aware of the event. Reporting required through the end of the study
	Provide all relevant source documentation (deidentified/ pseudonymized) for reported event.	
 Upon request of sponsor

Table 20-3: Investigator Reporting Requirements

Event Classification	Communication Method	Communication Timeline pre-market studies* (MEDDEV 2.7/3: CLINICAL INVESTIGATIONS: SERIOUS ADVERSE EVENT REPORTING UNDER DIRECTIVES 90/385/EEC AND 93/42/EEC)
Adverse Event including Adverse Device Effects	Complete AE CRF page, which contains such information as date of AE, treatment of AE resolution, assessment of seriousness and relationship to the device. Provide all relevant source documentation (deidentified/pseudonymized) for reported event as requested by sponsor.	
• In a timely manner (e.g. Recommend within 10 business days) after becoming aware of the information• Reporting required through 90-day follow-up visit• Upon request of sponsor

Abbreviations: AE=adverse event; CRF=case report form; UADE=unanticipated adverse device effect

* Please note that pre-market studies are clinical studies with investigational devices or with medical devices that bear the regulatory approval and are not being used for the same approved indications.

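### Primary safety is stated through 90 days, but the closing contact, where required non-serious event reporting ends, may fall anywhere from day 45 to day 135

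*Combined protocol and SAP*

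**What the plan says.** - **Period of the primary item.** Section 12.1.1 sets it as "Safety: All device- and procedure-related adverse events through 90 days post-implant procedure". The synopsis and Section 7 list the same item with no day limit.
- **Closing contact.** The synopsis plans a "90-day follow-up visit (to be conducted in clinic or by telephone at 90±45 days post-implant". Table 11-1 gives the same window, and Section 11.5.1 words it as "Ninety days (with ± 45 days visit window allowed) after the S-ICD implant and test procedure". Section 11.5.1 adds a chart review with no date of its own. Table 11-1 schedules nothing later.
- **End of participation.** Under Section 11.6, a subject's "participation in the study will end after completion of the 90-day follow-up visit". The synopsis also follows each subject only until that visit.
- **End of reporting.** In Table 20-3 the row for adverse events including device effects says "Reporting required through 90-day follow-up visit". The rows for serious adverse events, serious device effects, unanticipated (serious) device effects and device deficiencies run to the end of the study.
- **Collection text.** Section 11.1 says that reportable events "are reported on an ongoing basis and throughout a subject's participation of the trial". The adverse event row of Table 11-1 says "Collected throughout the trial starting from the time of the subject's enrollment". Section 20.1 requires that a reportable event, "whether prior to, during or subsequent to the study procedure, must be recorded in the paper CRF", and gives no end date.
- **Analysis.** Section 12.1.1 reports occurrence and percentage of related events from enrollment, with no closing day. Section 12.2.1 puts every Attempt, Partial Treatment and Treatment subject in the primary safety set.

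**The concern.** Safety is one of only two primary data items, and Section 12.1.1 gives it a fixed period. The schedule does not guarantee that period. A site can follow the plan exactly, close a subject at day 45 and have no further duty to report a non-serious related event in that subject. The subject still counts in the denominator as if followed for 90 days. In the other direction, a contact at day 135 can bring in events from the 45 days after the stated period, and nothing says whether they belong in the percentage.

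The events at stake are late, non-serious and related to the device or procedure. Table 19-2 lists infection, prolonged healing of the incision, hematoma or seroma, and nerve damage among the possible added risks of taking part; some of these may appear late or not meet the definition of serious. A reader of the final report who saw a 90-day percentage could not tell how many days it covers in each subject.

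**Working it through.** **Inputs.** Stated period: 90 days (Section 12.1.1). Contact window: 90±45 days (synopsis, Table 11-1, Section 11.5.1). End of required non-serious reporting: the contact itself (Table 20-3).

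**Window.** Earliest compliant contact: 90 − 45 = day 45. Latest: 90 + 45 = day 135. Follow-up under a fully compliant schedule can thus differ threefold (135/45 = 3).

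**Gap and excess per subject.** For a contact on day t, days of the stated period not guaranteed to be covered = max(0, 90 − t). Days observed beyond the period = max(0, t − 90).

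| Contact day | Not guaranteed | Share of 90 days | Beyond day 90 |
|---|---|---|---|
| 45 | 45 | 45/90 = 50% | 0 |
| 60 | 30 | 30/90 = 33% | 0 |
| 75 | 15 | 15/90 = 17% | 0 |
| 90 | 0 | 0% | 0 |
| 135 | 0 | 0% | 45 |

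These are shares of calendar time, not of events.

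**Does another passage close the gap?**
- Section 11.1 ties reporting to participation, which ends at the contact (Section 11.6), so it closes at the same point as Table 20-3.
- The adverse event row of Table 11-1 reads more widely, but it stands under Section 11.1 and the table has no later contact.
- Section 20.1 says which events must be recorded and sets no end; Table 20-3 supplies one.
- The chart review is described together with the contact. Without its own date it cannot be relied on to reach day 90.
- Section 12 has no rule for unequal follow-up or for events after day 90.

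**Study-level size.** This cannot be derived, since the documents give neither the timing of contacts nor event rates. Two illustrations, both on assumptions that are not in the plan:
- Contacts spread evenly over days 45 to 135. Mean days covered within the first 90 = [sum of 45 to 89, which is 3,015, + 46 × 90, which is 4,140] / 91 = 7,155/91 = 78.6 days, or 87% of 90.
- Constant event rate with true 90-day risk P. Risk seen by day 45 is 1 − (1 − P)^(45/90); by day 135 it is 1 − (1 − P)^(135/90). For P = 5%, 10% and 20% this gives 2.5%, 5.1% and 10.6% by day 45, and 7.4%, 14.6% and 28.4% by day 135.

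The second illustration takes every subject at one extreme of the window. Procedure-related events probably cluster early, so the real loss should be smaller.

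**The case against.** The strongest reply is that the phrase in Section 12.1.1 is shorthand for the visit, which the protocol itself names after day 90. The synopsis and Section 7 give no day limit, and the synopsis, Section 11.6 and Table 20-3 all end at that visit. This reading may well be the intended one, and it would remove the mismatch. But Section 12.1.1 does not say so, and even on this reading the percentage would mix follow-up of 45 to 135 days with no statement of how much each subject had.

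A second reply is that little is at stake, and much of this stands. Serious events, serious and unanticipated device effects and device deficiencies remain reportable to study end. The second electrode and the Y-Adapter are removed during the index procedure (Section 11.4). There is no hypothesis test, and neither futility trigger in Section 12.3.1 uses the safety percentage.

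A reader might also infer that the collection passages broadly contradict each other. The documents do not support that. Section 11.1, Section 11.6, Table 20-3 and the synopsis largely give one rule, and Section 20.1 merely lacks an end date. The row in Table 11-1 is loosely worded. What does not fit is the fixed period in Section 12.1.1.

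**Conclusion.** The point holds as a minor one. Followed as written, the plan can report a 90-day percentage for a primary item with as little as 45 days of assured ascertainment of non-serious related events in some subjects. It can also pick up events as late as day 135 in others, with no rule for them. Per subject the gap is 90−t days for a contact on day t before day 90, at most 45. Subjects contacted on or after day 90 have no gap.

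It would be wrong to conclude that half the events could be missed: the 50% is a share of days for the earliest possible contact, and the documents give nothing from which to derive a loss of events. Nor does the point extend to a general loss of serious events, whose reporting has a separate and later end. The judgment that the effect is probably small rests on early clustering of procedure-related events, which is an assumption, and on the removal of the investigational components at the index procedure, which the protocol states.

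**What to change.** **Simplest change.** Restate the safety item in Section 12.1.1 as running *through the 90-day follow-up visit (day 45–135)*, and report the distribution of follow-up days (for example median, range and number below 90) beside the percentages. This costs one sentence and one summary line and leaves the schedule alone.

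**Alternative.** Keep the 90-day period. For remaining subjects, hold the closing call or visit on or after day 90, within the existing day-135 limit, and list events after day 90 separately. This delivers the stated period. It costs flexibility in scheduling, changes the window text in the synopsis, Table 11-1 and Section 11.5.1, and may need an amendment with approval under Section 14. Enrollment was already under way at Revision C (14 enrolled, ten complete data sets), and the documents do not give the current count. Old and new windows would therefore be mixed, and follow-up days should be reported here too.

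**In either case.** Give the same end of adverse event collection in Section 11.1 with Table 11-1, Section 20.1 and Table 20-3, keeping the later end for serious events and device deficiencies explicit.

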5.2. Investigational S-ICD Y-Adapter

The Investigational S-ICD Y-Adapter (model 3598) is intended to facilitate ventricular fibrillation (VF) conversion testing of a novel S-ICD subcutaneous electrode configuration.

The Investigational S-ICD Y-Adapter is a sterile, single-use, acute implant accessory. It is intended for short-term use during a testing procedure and must be disconnected at the end of the testing procedure.

For the purpose of the investigational testing for this study, the S-ICD Y-Adapter connects two S-ICD subcutaneous electrodes to an S-ICD pulse generator. It consists of a long tail with an SQ-1 connector pin and a header with two SQ-1 connector ports.

The image consists of several black rectangular blocks of varying sizes. A large, solid black rectangle is centered in the middle of the frame, surrounded by a thin white border. Above this central rectangle is a smaller, solid black rectangle. The background is white, and there are thick black horizontal bars at the top and bottom edges. The overall composition is minimalist and abstract.

5.3. *Required Medical Equipment*

While not specifically part of the study system provided by Boston Scientific, additional equipment provided by the investigational center required for the study include:

- Back-up external defibrillator for emergency rescue
- Continuous blood pressure monitoring
- Fluoroscopic imaging equipment

6. Study Objectives

The primary objective of this acute feasibility study is to assess the defibrillation threshold (DFT) when adding a second left parasternal electrode to an S-ICD system 2-electrode configuration

The secondary objective is to assess the efficacy of 2-electrode configurations (Parallel and 90°) to convert VFJ.

The tertiary objective is to assess factors that influence the DFT when adding the second electrode (e.g. spacing and orientation or angle between electrodes).

7. Study Data

Primary Data:

- All device- and procedure-related adverse events
- The DFTs for the 2-electrode configuration (Parallel and 90°) consisting of two left-parasternal electrodes to left lateral PG

Secondary Data:

- The shock impedance for each of the two S-ICD shock configurations (one parasternal electrode and two parasternal electrodes)
- VF conversion success for the 2-electrode configuration (Parallel and 90°)

8. Study Design

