12.2. General Statistical Methods

12.2.1. Analysis Sets

Primary Safety analyses will include all Attempt, Partial Treatment, and Treatment subjects, as defined in Section 10.3.

Primary Effectiveness analyses will include all Treatment subjects.

Secondary Effectiveness analyses of one-electrode shock data will include both Partial Treatment and Treatment subjects. Secondary Effectiveness analyses of 2-electrode configuration (Parallel and 90°) shock data will include Treatment subjects.

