20.7. Subject Death Reporting

A subject death during the study should be reported to Boston Scientific within 24 hours of site notification. The site's EC must be notified of any deaths in accordance with that site's EC policies and procedures.

Notification of death must include a detailed narrative (death letter) that provides detailed information describing the circumstances surrounding the death. A death narrative in the local language is acceptable, if accompanied by a translation in English. The details listed below should be addressed in the death narrative, in order for Boston Scientific to understand the circumstance surrounding the death:

- Date and time of death
- Place death occurred
- Immediate cause of death
- Rhythm at the time of death, if known (include any available documentation)
- Whether the death was related to the pulse generator, electrode, Investigational S-ICD Y-Adapter, clinical investigation, procedure, or subject condition
- Whether or not the death was witnessed
- Device status and/or activity at the time of death (device recipients only – pacing and defibrillation, active or inactive)
- Whether the subject had worsening heart failure
- Any other circumstances surrounding the death
- Approximate time interval from the initiating event to death (temporal course). Items to consider include, but are not limited to: information regarding last time subject was seen by investigator, last office visit, etc.
- Investigator or sub-investigator signature and date

Also submit the following documentation:

If the subject expired in the hospital:

- A copy of the medical records for that admission (e.g., H&P, consults, test results, operative reports, and/or progress notes from the hospital chart)

- Death certificate (if available)
- Autopsy report (if applicable)

If the subject expired outside of the hospital (e.g., home):

- A copy of the most recent clinic visit (if not already submitted to Boston Scientific)
- Death certificate (if available)

Whenever possible, the PG should be interrogated. Leads and related Boston Scientific RM system components (e.g., PGs) should be removed intact and returned promptly to Boston Scientific RM for analysis. The Boston Scientific Medical Safety must review information regarding subject deaths.

21. Informed Consent

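### Section 12's only safety summary is limited to related events, so an SAE judged 'Not Related', and any death recorded as its outcome, falls outside it

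*Combined protocol and SAP*

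**What the plan says.** The safety result is stated in four places, each limited by relatedness.

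- Synopsis, Primary Safety Data: "All S-ICD system and procedure related adverse events".
- Section 7, Primary Data: "All device- and procedure-related adverse events".
- Section 12.1.1, Primary Data: "Safety: All device- and procedure-related adverse events through 90 days post-implant procedure".
- Section 12.1.1, Statistical Methods, the only bullet there on safety: "System and procedure related adverse events occurrence and percentage will be collected and reported", counted from enrolment.

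Section 12.2.1 sets the population: "Primary Safety analyses will include all Attempt, Partial Treatment, and Treatment subjects, as defined in Section 10.3". It says who is analysed and adds no type of event.

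The reporting sections are wider. Section 20.1 lists "All Serious Adverse Events regardless of cause" among the events that sites must report. It also says: "Death should not be recorded as an AE but should only be reflected as an outcome of ONE (1) specific SAE". Section 20.7 adds: "A subject death during the study should be reported to Boston Scientific within 24 hours of site notification". Under Section 20.3 the investigator assesses relatedness, and 'Not Related' is one of the four classes in Table 20-2.

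**The concern.** This is a single-arm, open study in which extra VF inductions and a second tunnelled electrode are added to a standard implant in one session. The planned safety summary applies a relatedness judgement before anything is counted, and that judgement is made by an investigator who knows what was done. Someone reading only the Section 12 summary could not tell how many SAEs or deaths the judgement had removed.

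The protocol does not filter its own urgent notifications this way. Sections 11.4.6 and 11.5.1 require 24-hour notice of death, of bleeding that needs treatment and of unplanned hemodynamic support, and 11.5.1 adds system infection. None of these carries a relatedness condition. What is at stake is how complete and transparent the descriptive safety result is; the effectiveness results do not depend on it.

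**Working it through.** The plan gives no safety figure to reproduce. Its one worked number, the exact 95% interval for 19 of 20 conversions (75.13% to 99.87%), recomputes correctly but concerns effectiveness. The check is therefore mainly a reading of the text.

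**Step 1: what is collected and what is summarised.**

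| Event | Collected? | In the Section 12 safety summary? |
|---|---|---|
| AE or SAE classed possibly, probably or causally related | Yes (20.1) | Yes |
| SAE classed 'Not Related' | Yes (20.1) | No |
| Death as outcome of a related SAE | Yes (20.1, 20.7) | Only through its SAE; no separate death count |
| Death as outcome of a 'Not Related' SAE | Yes (20.1, 20.7) | No |

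The last row follows from two rules taken together. Death is not an event in its own right (20.1), and the summary takes only related events (12.1.1). When the parent SAE is excluded, the death goes with it.

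**Step 2: does another part of the statistical plan fill the gap?** Section 12.2.1 names only the primary safety analyses and fixes the subjects. The secondary data in 12.1.1 are shock impedance and conversion success. The synopsis entry on statistical methods names summaries of DFT and VF conversion only. No secondary safety analysis is listed.

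**Step 3: how wide is the filter?** Table 20-2 classes weak links as 'Possibly Related', along with cases where relatedness cannot be assessed or information is missing. Only events positively judged 'Not Related' drop out.

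**Step 4: scale.** Under Sections 10.1 and 10.3, subjects who reach Attempt status count towards the ceiling of 42 and Intent subjects do not, so 42 is the largest safety set. A subject whose only SAE is judged 'Not Related' contributes:

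- to an all-cause SAE percentage: 1/42 = 0.0238, or 2.4 percentage points;
- to the planned related-event percentage, through that SAE: 0.

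With a smaller safety set the first figure is larger. The documents give no SAE rate and no split by relatedness, so the expected number of such subjects cannot be derived from them.

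**The case against.** The strongest reply is that related events are a reasonable primary safety measure here. The study is a pilot with no hypothesis. The adapter and second electrode are removed before the procedure ends, and the subject leaves with a commercial system (Section 10.4). Relatedness covers the whole S-ICD system and the procedure, and doubtful cases stay in. What drops out is the least informative about a temporary intra-operative test, and without a comparator an all-cause rate cannot be attributed to anything. All of this stands, and it is why the related-event summary should be kept. It does not explain why events already on the CRF should go uncounted beside it.

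A reader might infer that unrelated SAEs and deaths will go unseen. The documents do not support that:

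- Medical Safety must review information on deaths (20.7).
- The DMC, whose members take no part in the study, reviews aggregate data and has access throughout (22.2).
- Adverse event information goes to investigators and authorities as applicable (20.6).
- All enrolled subjects must be accounted for (10.2).
- A Clinical Investigation Report will be issued (24.2). Its safety content is not specified, so it may include all-cause events, but the plan does not commit to that.

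A reader might also infer that the sponsor's safety team decides relatedness. Section 22.1 says only that the team evaluates events and classifies them into categories outlined earlier. It neither names relatedness nor says that the team may override the investigator, to whom Section 20.3 gives that assessment.

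**Conclusion.** The point holds for Section 12 and no further. Followed as written, its descriptive safety summary leaves out SAEs that the investigator judges 'Not Related' and any deaths recorded as their outcome, although both are collected. This is a filter written into the plan, not merely a detail left open.

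The gap lies in the specified summary. Data collection and oversight during the study are unaffected. No DFT, impedance or conversion estimate and no futility trigger changes, and the plan states no death count that would be wrong. Whether readers of the final report would miss such events cannot be settled from the documents.

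The size is 2.4 percentage points per affected subject at the ceiling of 42, with the number of such subjects unknown. That weight assumes the full 42 enter the safety set and that the subject has no other SAE. Severity is minor. Confidence is high that Section 12 omits these events; no claim is made about how often they will occur.

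**What to change.** In Section 12.1.1, keep the related-event summary and add, for the existing safety set of Attempt, Partial Treatment and Treatment subjects:

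1. the number and percentage of subjects with any SAE, regardless of relationship;
2. the number of deaths from any cause;
3. a listing of each such event with its timing and assigned relatedness.

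Label these figures descriptive and not attributable to the device or procedure, because there is no comparator.

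The cost is a short addition to the text, one table and one listing, from data that Sections 20.1 and 20.7 already require. No new data, visits or subjects are needed. The downside is that the displayed event rate may look less favourable and cannot be interpreted causally.
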